**ONLY ASK IF STATUS OF PATIENT IS KNOWN**

**If it's okay, I would like to ask you some questions about \_\_\_\_'s status and your struggles and efforts to support \_\_\_\_ with this.**

1. First, can you tell me when/how you learned about \_\_\_\_'s HIV status? How was that experience for you? (Stigma, fear, friends/family response, reaction)
  - a. How has \_\_\_\_'s HIV status affected your life in this family?
    - i. PROBE: has this had any effect on your relationship within your family?
  - b. Can you talk about whether \_\_\_\_'s status has had any impact on your role in the community? What about \_\_\_\_'s role in the community?
2. What form of treatment has \_\_\_\_ been getting since diagnosis, to your knowledge?
  - a. What is it that has worked well for \_\_\_\_ with the treatment he/she is taking?
  - b. What has not been working well? (type or combination of drugs, changing from first line to second line treatment, taking tuberculosis treatment too, etc.)
3. Now I would like to talk to you about access to care for (name of the patient).
  - a. Where did \_\_\_\_ access his/her care from? Can you talk about any changes in how \_\_\_\_ accessed care over time?
  - b. Apart from getting care from the clinic, are there other places and forms of treatment where \_\_\_\_ got care?
    - i. Probe about traditional medicine, faith healing.
    - ii. How has this affected his/her journey on treatment?
  - c. What, if anything, seemed to work well for \_\_\_\_'s HIV care?
  - d. What did you encourage \_\_\_\_ to do? What did others encourage \_\_\_\_ to do?
4. **(If the patient learned their HIV status before hospitalization):** Many people have a difficult time accessing and staying in HIV care or on treatment. For many, the challenges they face with staying on ART lead them to be unable to take treatment every day or even stop taking it. Can you describe any experiences \_\_\_\_ has had with this?
  - c. Can you talk about any challenges \_\_\_\_ faced with taking ART?
    - i. Challenges at home/In household? Community?
    - ii. Concerns with taking it because of advice received (from family, friends, church)
    - iii. Challenges with clinic / accessing drugs? (Stigma, time, cost, distance, rude staff)
    - iv. Challenges/barriers within yourself (acceptance of status, motivation, beliefs, fears, side-effects, what others might think etc.)
  - d. Now, among all of the reasons you have just mentioned, which of these reasons would you say mattered the most. What makes you say that? (rank exercise)
  - e. Was \_\_\_\_ about to overcome any of these challenges? If Yes: how? If no, what could help you to overcome these challenges?
  - f. Were you able to help \_\_\_\_ overcome any of these challenges? (If yes, can you talk about how you were able to support \_\_\_\_ to overcome the challenges?)
  - g. Are there other resources you would need to help \_\_\_\_ overcome some of these challenges? Can you talk about that?

11. Thank you very much for your time. Do you have any questions or comments before we close this interview? Is there anything that you would like us to talk about that which we have not talked about which you think is important for (name of the patient) that can help him get better or do well on his treatment journey?

## **17. Appendix 4: CHW, CLO, Clinicians Interview Guide**

### **Interview with CHW, CLO, Clinicians**

#### **Endline, ReCharge Interview with CHW, CLO, Clinicians (hospital, clinic)**

Interviews with providers involved in ReCharge.

1. To help understand more about your involvement in Recharge broadly, tell me your responsibilities in this intervention. What role did you play with caring for patients LHIv who had been hospitalized and then discharged following their discharge?
2. To understand how this program worked and its weaknesses, let's talk more specifically about examples of two patients you worked with. Think of one that worked out well. Think of one that did not. (each question to be asked for both types of patient).
  - a. Talk about your first encounter with this patient. How did it go? Where was it? What did you learn? What did you do to help them?
  - b. Talk about your first visit with them after discharge? How did it go? Where? What happened?
  - c. Talk about other calls, supports you provided? What happened? What did you do, how did they respond?
  - d. Talk about what you learned about what the patient needed, how did you support that?
  - e. Talk about the patient's involvement in care after discharge? What services did they get? Where? How?
  - f. Talk about your role with anyone else in the patient's life – caregiver? Children? Others?
  - g. Talk about how you supported the patient's recovery?
  - h. Tell me what you think was the most important contribution you made to this patient's recovery?
    - i. Tell me what you think enabled / prevented them from recovering?
    - j. What else could the program have done to better support this patient?
    - k. (for patient that did not go well) What explains, in your mind, why this patient did not do well/recover?
      - i. What would the program change to help patients like this one to do better in the future?
3. What are your recommendations for how CHWs should work with hospital to help discharged HIV patients?
4. What are your recommendations for how CHWs should work with clinics to help discharged HIV patients?
5. What are your recommendations for how CHWs should facilitate relationship between hospitals and clinics to help discharged HIV patients?

**22. Appendix 9: Patient Health Questionnaire 9 (PHQ-9): Nyanja**

Pa milonga iwiri yapita, kodi ni kangati kamene munavutisidwa ndi yali mavuto aya yokonkapo?			
(Chongani mu kabokosi kuti muonese yankho yanu)			
1	Kukondwera pang'ono kapena kusangalala kung'ono mukuchita zinthu	 0.Kulibe ngankhale pang'ono  1.Masiku angapo  2.Kupambana pa hafu ya masiku  3.Pafupi-fupi masiku onse	
2	Kumvera kuipa, wodidikizidwa mu maganizo, kapena wopanda chiyembekezo	 0.Kulibe ngankhale pang'ono  1.Masiku angapo  2.Kupambana pa hafu ya masiku  3.Pafupi-fupi masiku onse	
3	Kuvutika kugona kapena kusagona, kapena kugona kwambiri	 0.Kulibe ngankhale pang'ono  1.Masiku angapo  2.Kupambana pa hafu ya masiku  3.Pafupi-fupi masiku onse	
4	Kumvera kulema kapena kunkhala ndi mphamvu zing'ono	 0.Kulibe ngankhale pang'ono  1.Masiku angapo  2.Kupambana pa hafu ya masiku  3.Pafupi-fupi masiku onse	
5	Kunkhala ulibe chilakolako chakudya safuna kapena kudya kwambiri	 0.Kulibe ngankhale pang'ono  1.Masiku angapo  2.Kupambana pa hafu ya masiku  3.Pafupi-fupi masiku onse	
6	Kumvera kuipa pa za inu mweka -- kapena kuti munakangiwa kapena munazilekelela kapena kulekelela banja	 0.Kulibe ngankhale pang'ono  1.Masiku angapo  2.Kupambana pa hafu ya masiku  3.Pafupi-fupi masiku onse	
7	Kuvutika kuika maganizo pamodzi pa zinthu, monga kuwerenga nyuzipepa kapena kuonelela TV	 0.Kulibe ngankhale pang'ono  1.Masiku angapo  2.Kupambana pa hafu ya masiku  3.Pafupi-fupi masiku onse	
8	Kuyenda kapena kukamba pang'ono-pang'ono kwambiri Kwamene mwina munaona? Kapena zosiyanako – kunkhala Kusankhazikika kapena kusapumula kuti munali kuyenda-yenda kwambiri kupambana nthawi zonse	 0.Kulibe ngankhale pang'ono  1.Masiku angapo  2.Kupambana pa hafu ya masiku  3.Pafupi-fupi masiku onse	

9	Maganizo yakuti chingankhale bwino kufa kapena Kuzichita mweka mu njira iliyonse	 0.Kulibe ngankhale pang'ono  1.Masiku angapo  2.Kupambana pa hafu ya masiku  3.Pafupi-fupi masiku onse
	Score "Masiku angapo".	
	Score "Kupambana hafu ya masiku":	
	Score "Pafupi-fupi masiku onse":	
	Enter Total Score:	
10	Ngati mwachonga mavuto yali yonse, kodi aya mavuto; Yachipanga bwanji kunkhala chovuta kwa inu kuchita nchito zanu; Kusamalira zinthu pa nyumba kapena kumverana ndi anthu ena? with other	 0.Sichokosa ngankhale pang'ono  1.Nichokosako  2.Ni chokosa kwambiri difficult  3.Nichokosa kwambiri
	Does the hard copy score match the database score?	 Yes  No
	If the scores do not match, please comment	<hr/> <hr/>
	Date form completed: (DD/MM/YYYY)	
	Form Completed by (initials):	

**23. Appendix 10: Patient Health Questionnaire 9 (PHQ-9): Bemba**

Pa milungu ibili iyapita bushe miku inga iyo mwacushiwapo namafya ayali fyонse ayakonkelepo aya? (Click the circle to indicate your answer)			
1	Ukutemwa ukunono nangu ukusekelamo mukucita ifintu	 0.Awe nelyo panono  1.Inshiku ishingiko  2.Ukucila pali hafu ya nshiku  3.Mupepi na cila bushiku	
2	Ukushisansamuka, ukutitikishiwa nangu ukushikwata isubilo	 0.Awe nelyo panono  1.Inshiku ishingiko  2.Ukucila pali hafu ya nshiku  3.Mupepi na cila bushiku	
3	Ubwafya bwakulala nangu ukulalisha nangu ukulalisha sana	 0.Awe nelyo panono  1.Inshiku ishingiko  2.Ukucila pali hafu ya nshiku  3.Mupepi na cila bushiku	
4	Ukumfwa uwanaka nangu ukukwata amaka ayanono	 0.Awe nelyo panono  1.Inshiku ishingiko  2.Ukucila pali hafu ya nshiku  3.Mupepi na cila bushiku	
5	Ukushifwaya ukulya nangu ukulya sana	 0.Awe nelyo panono  1.Inshiku ishingiko  2.Ukucila pali hafu ya nshiku  3.Mupepi na cila bushiku	
6	Ukumfwa ububi palwa mwebene mweka – nangu ukuti mwalifilwa nangu mwalilekelesha nangu mwalilekesha ulupwa	 0.Awe nelyo panono  1.Inshiku ishingiko  2.Ukucila pali hafu ya nshiku  3.Mupepi na cila bushiku	
7	Ubwafya bwakubika amaano pa fintu, pamo nga ukubelenga nyunshipepa nangu ukutamba TV	 0.Awe nelyo panono  1.Inshiku ishingiko  2.Ukucila pali hafu ya nshiku  3.Mupepi na cila bushiku	
8	Ukwenda nangu ukulanda panono-panono sana icakuti; Bambi kuti baishiba? Nangu ukupilibula – ukuba uushiteka umutima pansi umutima pansi icakuti mwaleenda-enda sana ukucila lyonse	 0.Awe nelyo panono  1.Inshiku ishingiko  2.Ukucila pali hafu ya nshiku  3.Mupepi na cila bushiku	
9	Amatontonkanyo ayakuti kuti caba bwino nga mwalifwile nangu ukuicena mwebene munshila imbi	 0.Awe nelyo panono  1.Inshiku ishingiko  2.Ukucila pali hafu ya nshiku	

		 3.Mupepi na cila bushiku
	Score "Several days"	
	Score "More than half the days"	
	Score "Nearly every day"	
	Enter Total Score:	
10	Nga cakutila mwaconga amafya ayali yonse, bushe aya mafya yalengele ukuba icayafya kuli imwe ukucita imilimo, Ukusakamana ifintu pa ng'anda, nangu ukumfwana nabantu bambi	 0.Sichokosa ngankhale pang'ono  1.Nichokosako  2.Ni chokosa kwambiri difficult  3.Nichokosa kwambiri
	Does the hard copy score match the database score?	 Yes  No
	If the scores do not match, please comment	_____
	Date form completed: (DD/MM/YYYY)	
	Form Completed by (initials):	

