**24. Appendix 11: Patient Health Questionnaire 9 (PHQ-9): English**

In the past two weeks, how many times have you been bothered by these problems? (Click the circle to indicate your answer)			
1	A little interest or pleasure in doing things	 0.Not at all  1.A few days  2.More than half a day  3.Almost everyday	
2	. Feeling down/bad, depressed, or hopeless	 0.Not at all  1.A few days  2.More than half a day  3.Almost everyday	
3	Difficulty falling asleep or staying asleep, or sleeping too much	 0.Not at all  1.A few days  2.More than half a day  3.Almost everyday	
4	Feeling tired/weak or having little energy	 0.Not at all  1.A few days  2.More than half a day  3.Almost everyday	
5	Poor appetite or overeating	 0.Not at all  1.A few days  2.More than half a day  3.Almost everyday	
6	Feeling bad about yourself or that you are a failure or let yourself or your family down	 0.Not at all  1.A few days  2.More than half a day  3.Almost everyday	
7	Difficulty/trouble concentrating on things, such as reading or watching TV	 0.Not at all  1.A few days  2.More than half a day  3.Almost everyday	
8	Moving or speaking very slowly that other people could have noticed or the opposite – being so fidgety or restless that you have been moving around a lot more than usual	 0.Not at all  1.A few days  2.More than half a day  3.Almost everyday	
9	The idea that it would be better to die or to do it yourself in any way	 0.Not at all  1.A few days  2.More than half a day	

		 3.Almost everyday
	Score "Several days"	
	Score "More than half the days"	
	Score "Nearly every day"	
	Enter Total Score:	

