10	If you checked off any problems, how difficult has these problems made it for you to do your job, take care of things at home, or get along with other people?	 0. Not difficult at all  1. A bit difficult  2. Difficult  3. Very difficult
	Does the hard copy score match the database score?	 Yes  No
	If the scores do not match, please comment	<hr/> <hr/>
	Date form completed: (DD/MM/YYYY)	
	Form Completed by (initials):	

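### Scored item 8 of the Nyanja PHQ-9 appears to ask a different question from the English and Bemba forms; separately, item 10 on the Bemba form carries Nyanja answers, and its two highest levels read alike on both local-language forms

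*Combined protocol and SAP*

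**What the plan says.** **Item 8 (scored).** The English form (Appendix 11) asks about "Moving or speaking very slowly that other people could have noticed". The Bemba form (Appendix 10) has "Bambi kuti baishiba" at the same place. The Nyanja form (Appendix 9) has "Kwamene mwina munaona".

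**Item 10 (not scored).** The English stem begins "If you checked off any problems, how difficult has these problems made it for you to do your job", and its answers at levels 2 and 3 are distinct: difficult, then very difficult. The Bemba stem is in Bemba and ends "nangu ukumfwana nabantu bambi". Its answers, however, start at "0.Sichokosa ngankhale pang'ono" and finish with "2.Ni chokosa kwambiri difficult" and "3.Nichokosa kwambiri". The Nyanja form prints the same four answers.

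**Use of the score.** Depression level after the intervention is secondary endpoint 6 in section 4.5. Prevalence of depression and of behavioural health comorbidities is an exploratory aim (section 4.3, nos. 2 and 5). Section 5.3.2 uses a PHQ-9 score of 10 or more, with referral, as one route into up to 8 additional endline interviews. Section 5.2.4 places the screening at one month. No section describes back-translation or a check that the three versions agree. The line on each form comparing the hard-copy and database scores checks data entry, not wording.

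**The concern.** A PHQ-9 total pooled over three language forms means one thing only if each scored item asks the same question on each form. If Nyanja item 8 asks for the respondent's own observation while the other two forms ask what others could have seen, totals near the cut depend partly on which form was used. At stake are a listed secondary endpoint, the prevalence aims and the interview selection rule.

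Item 10 is a lesser matter. Respondents on the Bemba form are offered answers in another language, and on both local-language forms the wording does not distinguish the two highest levels of difficulty.

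**Working it through.** The plan states no figure to reproduce. The check compares the forms, then bounds the effect on the score.

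**1. Item 8, using the forms' own vocabulary.**

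| Form | Who notices | Internal evidence |
|---|---|---|
| English | Other people | Stated outright |
| Bemba | Others (*Bambi*) | *bambi* recurs in item 10 where the English says other people |
| Nyanja | Apparently the respondent (*munaona*) | *muna-* addresses the respondent in the lead question (*munavutisidwa*) and in item 6 (*munakangiwa*, *munazilekelela*); the form's phrase for other people, *anthu ena*, is in item 10 but not in item 8 |

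This supports a mismatch but does not prove the translation.

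**2. Bound on the total.** Nine items scored 0 to 3 give a maximum of 9 × 3 = 27. Item 8 is 3/27 = 11% of that range. Let *s* be the sum of the other eight items and *x* the item 8 score. Item 8 can decide whether *s* + *x* ≥ 10 only if *s* < 10 and *s* + 3 ≥ 10, so *s* must be 7, 8 or 9:

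- *s* = 9: the cut is reached if *x* is at least 1.
- *s* = 8: the cut is reached if *x* is at least 2.
- *s* = 7: the cut is reached only if *x* = 3.

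For any other *s*, item 8 cannot change the classification. This takes the section 5.3.2 cut as 10 or more.

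**3. Item 10 answers.** Comparing the strings, 4 of 4 Bemba answers are identical to the Nyanja answers. They are out of language on the Bemba form. The level 0 answer shares *ngankhale pang'ono* with the Nyanja not-at-all option, whereas Bemba items 1 to 9 use *Awe nelyo panono*. Levels 2 and 3 use *kwambiri*, the Nyanja form's word in items 3 and 5 (too much sleep, overeating), where the Bemba form has *sana*. Once the space and the stray *difficult* are removed, levels 2 and 3 are the same string, so four numbered levels carry three distinct wordings.

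**4. Reach of item 10.** On all three forms the total is entered after item 9 and before item 10, so item 10 adds 0 points. No objective, endpoint or analysis in sections 4, 5.2.4 or 8.2.1 uses functional difficulty.

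**5. A related mismatch on the English form.** Its level 2 frequency option speaks of half a day, while its own scoring row speaks of half the days. That option appears on all nine scored items, so aligning Nyanja and Bemba with English would not by itself make totals comparable.

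**The case against.** The strongest reply is that the certain part does not matter and the part that matters is not certain. Item 10 is plainly misprinted but unused. Item 8 is scored, but the reading rests on translating one clause in a line that is visibly broken. Both points stand and set the scope here: item 10 is a form correction, and item 8 needs a native speaker's confirmation. Errors in reading the PDF could alter letters or line breaks, but would not carry whole Nyanja phrases into the Bemba answers.

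There is also some mitigation. The item 10 options stay numbered in rising order, and section 7.1 describes a research team fluent in all three languages. This softens the duplicated wording without curing it.

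Three stronger readings are tempting and are not supported:

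- *The Nyanja wording is easier to meet, so Nyanja totals run high.* Nothing shows this. In every language the respondent makes the judgement, and the restlessness half of the English item has no observer condition.
- *The comparison with historical controls is biased.* Section 5 says in general that secondary outcomes will be compared with the earlier group, but section 8.2.1 specifies no PHQ-9 comparison. Section 5.2.2 has controls meet the same criteria and be recruited in the same way. The language mix is not given for either group.
- *The item 10 fault distorts the depression score.* It cannot, because item 10 is not summed.

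It is also fair to say that the synopsis omits mental health from its secondary endpoints, and that a purposive sample of up to 8, with AUDIT-C as an alternative route, does not need exact score equivalence. The section 4.5 endpoint and the prevalence aims remain.

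**Conclusion.** The point holds within limits. Nyanja item 8 appears to differ in meaning from the other two forms, subject to a Nyanja speaker's confirmation. Any effect on a total is at most 3 of 27 points, and on the 10-or-more classification it is confined to respondents with 7 to 9 points on the other eight items. Neither direction nor size can be determined, because the documents give no language mix and no score distribution. The item 10 faults are certain on the page and affect only that item. None of this touches the viral suppression, mortality or retention outcomes. It is worth correcting because depression level is a listed endpoint and the correction is small.

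**What to change.** 1. Have a Nyanja speaker confirm item 8 and reword it to refer to other people.
2. Put Bemba answers on Bemba item 10.
3. On both local-language forms, give item 10 levels 2 and 3 distinct wording that matches the English difficult and very difficult.
4. Back-translate every changed line.
5. In the same pass, reconcile the English level 2 frequency option with that form's own scoring row.

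If forms are already in use, record the form language for each interview, combine item 10 levels 2 and 3 for Nyanja and Bemba forms, and show PHQ-9 results by form language.

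The cost is a few lines of translation and an ethics notification of the revised forms, since section 9.2 puts protocol modifications before the review boards. Sample size and visit schedule are unaffected.

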**24. Appendix 11: Patient Health Questionnaire 9 (PHQ-9): English**

In the past two weeks, how many times have you been bothered by these problems? (Click the circle to indicate your answer)			
1	A little interest or pleasure in doing things	 0.Not at all  1.A few days  2.More than half a day  3.Almost everyday	
2	. Feeling down/bad, depressed, or hopeless	 0.Not at all  1.A few days  2.More than half a day  3.Almost everyday	
3	Difficulty falling asleep or staying asleep, or sleeping too much	 0.Not at all  1.A few days  2.More than half a day  3.Almost everyday	
4	Feeling tired/weak or having little energy	 0.Not at all  1.A few days  2.More than half a day  3.Almost everyday	
5	Poor appetite or overeating	 0.Not at all  1.A few days  2.More than half a day  3.Almost everyday	
6	Feeling bad about yourself or that you are a failure or let yourself or your family down	 0.Not at all  1.A few days  2.More than half a day  3.Almost everyday	
7	Difficulty/trouble concentrating on things, such as reading or watching TV	 0.Not at all  1.A few days  2.More than half a day  3.Almost everyday	
8	Moving or speaking very slowly that other people could have noticed or the opposite – being so fidgety or restless that you have been moving around a lot more than usual	 0.Not at all  1.A few days  2.More than half a day  3.Almost everyday	
9	The idea that it would be better to die or to do it yourself in any way	 0.Not at all  1.A few days  2.More than half a day	

		 3.Almost everyday
	Score "Several days"	
	Score "More than half the days"	
	Score "Nearly every day"	
	Enter Total Score:	
10	If you checked off any problems, how difficult has these problems made it for you to do your job, take care of things at home, or get along with other people?	 0. Not difficult at all  1. A bit difficult  2. Difficult  3. Very difficult
	Does the hard copy score match the database score?	 Yes  No
	If the scores do not match, please comment	<hr/> <hr/>
	Date form completed: (DD/MM/YYYY)	
	Form Completed by (initials):	

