### **4.5 Secondary Endpoints – HIV cascade and clinical outcomes**

1. HIV viral load at 6 months post-discharge.
2. Readmission to hospital within 6 months of discharge
3. Mortality within 6 months of discharge.
4. Retention in HIV care after discharge defined by no gap of >28 days off ART from discharge date to 6 months post-discharge date.
5. Engaged in ART care at a community (non-referral site) clinic at 6 months post-discharge
6. Mental health outcomes (i.e. depression level) post intervention

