- Distance to referral health clinic and to referring hospital (time takes to get to clinic / mode of transit)

At one month:

- Mental health screening (PHQ)
- Alcohol screening (AUDIT)
- Household food insecurity (HFIES scale)
- Household asset-based wealth index (DHS module)

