At the six-month follow-up, we will re-interview up to 16 of these 24 for a second IDI reflecting on patient experience and capturing their perceptions of whether and how CHW follow-up addressed barriers or enhanced enablers to care to assess feasibility and acceptability. We will work with CLOs, CHWs, and clinic-level data to stratify the endline sample by patient outcome (retained versus not retained), and purposively select patients within strata to capture a range of demographic and facility-level characteristics. The same interviewer who interviewed the patient at time 1 will return to complete the interview at time 2. Again these interviews would take place at a time and place convenient for the patient. The interviewer will then ask the patient for permission to invite their primary caregiver to be interviewed as well. If the patient and the caregiver consent, then the interviewer will also interview the care giver. Caregiver IDIs will address the experience of caring for the discharged patient throughout the intervention and their perceptions of CHW follow-up. When non-retained participant deaths are ascertained, we will try to perform an IDI with the caregiver (after reasonable time elapses for mourning) to understand the barriers to care, co-morbidities and other mortality causes (we estimate up to 4 such cases based on COLAH); we may therefore have more caregiver than patient endline interviews.

In addition to the longitudinal sub-sample of 16 patients stratified by re-engagement in care outcomes; we will also purposively sample up to 8 patients (for a total of up to 24 endline interviews) who showed signs of mental illness or behavioral health concerns (i.e., scored above  $\geq 10$  points on the PHQ-9 screening tool for depression and related concerns; or scored above  $\geq 3$  on the AUDIT-C), and were referred by the team for mental health services. We will interview these patients to understand experiences of patients with mental health related challenges such as depression and alcohol abuse, and to assess how the referral process and related services were received by such patients. These interviews will be essential toward preparing for future work with patients experiencing similar challenges.

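### English PHQ-9 item 1 literally says that some interest is present, so in English-form interviews this one item can be mis-scored (minor)

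*Combined protocol and SAP*

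**What the plan says.** Appendix 11 gives the English PHQ-9. The stem is "In the past two weeks, how many times have you been bothered by these problems", and item 1 under it is "A little interest or pleasure in doing things". Each of the nine items is scored from 0 (not at all) to 3 ("3.Almost everyday"), and the form ends with a line marked "Enter Total Score". Item 4 is "Feeling tired/weak or having little energy", where the word *little* stands without an article.

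The score is used in these places:

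- Section 5.2.4 lists the PHQ among the one-month measures, and section 5.1 has the community health worker screen for depression at about one month.
- Section 4.5 makes "Mental health outcomes (i.e. depression level) post intervention" the sixth secondary endpoint.
- Section 4.3 (exploratory objectives 2 and 5) asks for the prevalence of behavioral and mental health comorbidities, with depression named in objective 5.
- Section 5.3.2 selects up to 8 patients for interview, one route being a score of 10 or more "points on the PHQ-9 screening tool for depression and related concerns".

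Section 4.5 does not name the instrument behind its depression endpoint. The PHQ-9 is the only depression scale supplied, so I take it to be the PHQ-9.

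**The concern.** Eight of the nine items name a complaint, and answering that it occurs often raises the score. Item 1, taken word for word, names something that is present and mildly positive. It is still scored in the same direction as the others, with no reverse-coding rule and no interviewer instruction.

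A patient who has lost all interest and reads the item literally would answer that it applies not at all and score 0, where the intended item would give 3. A patient who has some interest almost every day would score 3. If that patient's interest is in fact normal, the intended item would give 0.

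The stake is measurement quality: one item adds error to the total, and some patients near 10 points land on the wrong side. The error cannot be undone at analysis, because a recorded answer does not show how the patient understood the words.

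**Working it through.** The plan states no figure on this point, so there is none to reproduce. The check is a comparison of wording followed by a bound on the score.

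**Wording, within Appendix 11**

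- Item 1: *a little* with interest or pleasure, which literally means that some is present.
- Item 4: *little* with energy, which means that it is lacking.
- Stem: the items are problems that bothered the patient. This points to the deficit sense for item 1 but does not change its words.

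The form therefore uses the deficit phrase correctly in one item and departs from it in another.

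**Bound on the score**

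Inputs: nine items scored 0 to 3 (Appendix 11); threshold of 10 or more (section 5.3.2).

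- Largest total: 9 × 3 = 27.
- Let R be the sum of items 2 to 9, from 0 to 8 × 3 = 24. Let t be the score on item 1 as intended and o the score recorded.
- Correct total T = R + t; recorded total O = R + o; error O − T = o − t, which lies between −3 and +3.

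**Crossing upward** (T at most 9, O at least 10). Since O is at most T + 3, T must be at least 10 − 3 = 7. The correct totals that can cross are 7, 8 and 9. The extreme case is R = 7, t = 0, o = 3, which gives 7 → 10.

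**Crossing downward** (T at least 10, O at most 9). Since O is at least T − 3, T must be at most 9 + 3 = 12. The correct totals that can cross are 10, 11 and 12. The extreme case is R = 9, t = 3, o = 0, which gives 12 → 9.

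**One-step errors** matter only at the edge: R = 8, t = 1, o = 2 moves 9 → 10, and R = 8, t = 2, o = 1 moves 10 → 9.

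Totals of 0 to 6 and of 13 to 27 cannot change side because of this item.

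**What the other eight items settle.** If R is 10 or more, T is at least 10 whatever item 1 should have been. If R is 6 or less, T is at most 6 + 3 = 9. Only forms with R of 7, 8 or 9 leave the classification dependent on item 1.

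The number of patients affected would need the share interviewed in English, the share who read item 1 literally, and the distribution of totals. The documents give none of these.

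**The case against.** The strongest reply is the stem. Patients are asked how often problems bothered them, and someone who enjoys things is not bothered by doing so. Most respondents may therefore supply the intended meaning. The form also appears to be handled by staff, since it has a line for the initials of the person completing it, and a worker can explain an item. Nyanja and Bemba versions exist, so only part of the sample meets the English words. A patient with only a little interest on most days may truly have reduced interest, in which case 3 points is not clearly wrong.

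Much of this stands. It makes mis-scoring a risk rather than an expected result, and it makes the patient with no interest who scores 0 the clearer example. It does not repair the item: nothing tells the worker to explain it, and the form's instruction to click an answer leaves the mode of completion unclear. The sentence is complete and grammatical, so a text-extraction fault is an unlikely explanation.

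Stronger readings are tempting, but the documents do not support them:

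- *Well patients will be scored as depressed, or the scale is reversed.* The stem works against this, and at most one item of nine is involved.
- *The comparison with historical controls is biased.* Section 5 says in general that secondary outcomes will be compared, but section 8.2.1 defines no PHQ-9 contrast. Nothing shows that use of the English form differs between the groups.
- *The 10-point value is an analysis threshold.* Section 5.3.2 writes it as a criterion for purposive interview sampling, with an alcohol score as an alternative route.
- *The feasibility endpoint on seeking services after referral is distorted.* The documents state no separate PHQ-9 score that triggers referral, so a link is possible but not established.
- *The Nyanja and Bemba forms share the fault.* Their item 1 was not assessed here.

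**Conclusion.** The point holds as a minor wording error on a data-collection form. Item 1 of the English PHQ-9 is ambiguous on its face, inconsistent with item 4, and not corrected anywhere in the documents. The effect is confined to English-form interviews and to one item. The bound is 3 points of 27 in either direction, with correct totals of 7 to 12 open to reclassification in extreme cases and an unknown frequency.

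This rests on three assumptions: that the total is the plain sum of the nine items, that the threshold means 10 or more, and that the depression endpoint and prevalence objectives use this scale. It bears on the screen, that endpoint, those objectives and the choice of interviewees. It has no bearing on survival with viral suppression or on the sample size.

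**What to change.** Before the form is used:

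1. Delete the leading article from item 1 of Appendix 11, so that the item begins with *Little* and matches item 4.
2. Check the corrected item against the source instrument rather than adopting a new phrase.
3. Have a fluent speaker confirm that item 1 of the Nyanja form (Appendix 9) and of the Bemba form (Appendix 10) expresses a lack of interest.
4. If any English interviews have already been done with the printed item, flag them in the database. Report totals with and without item 1 for those records, and treat the 10-point classification as uncertain only where items 2 to 9 sum to 7, 8 or 9.

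The cost is one word on one form plus a short translation check. Section 9.2 sends modifications to ethics review, so the change can travel with the next submission if that comes before the form is used. No endpoint definition or sample size needs to change.
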